### 11.1. Safety Parameters

#### 11.1.1. Demographic Information

Subject demographic and baseline characteristic data to be collected on all subjects at the screening visit include date of birth, age, sex, race, and predominant ethnicity.

### **11.1.2. Medical History**

Relevant medical history, including SCD genotype, and current medical conditions will be recorded for all subjects at the screening and baseline visits, and will include all prior therapies for the treatment of SCD.

### **11.1.3. Vital Signs**

Vital sign measurements will be obtained at the time points specified in the Schedule of Assessments ([Table 6](#) for Part A and [Table 7](#) for Part B) and include body temperature, systolic and diastolic blood pressure, pulse rate, respiratory rate, and pulse oximetry. All vital sign measurements will be taken in the sitting position after the subject has been resting for 5 minutes. Vital signs should be taken before any blood samples are drawn.

### **11.1.4. Weight and Height**

For all subjects enrolled in Parts A and B, weight (kg) will be documented at the baseline (Day - 1) and the 1-week follow-up visit (Day 7 to 10). Subject height (cm) will be measured at the baseline visit.

### **11.1.5. Physical Examination (Complete and Symptom-directed)**

A complete physical examination will be performed for all subjects at screening, baseline (Day - 1), and 1-week follow-up visit (Day 7 to 10), for all subjects enrolled in Parts A and B. Complete physical examinations will include general appearance, skin, neck (including thyroid), eyes, ears, nose, throat, lungs, heart, abdomen, back, lymph nodes, extremities, vascular, and nervous system, and will be conducted at the screening visit. Information for each physical examination must be included in the source documentation at the study site and will be recorded on the eCRF.

A pretreatment directed physical examination will be performed on treatment Day 1 of Part A and on treatment Days 1 and 2 of Part B. All directed physical examinations will be symptom-based.

Any physical examination abnormality deemed clinically significant by the Investigator during screening will be reported as medical history. Any physical examination abnormality that emerges or has worsened after signing the ICF assessed as clinically significant by the Investigator will be reported as an AE.

### **11.1.6. Electrocardiogram**

A single recording baseline 12-lead electrocardiogram (ECG) will be obtained for all subjects at screening. Subjects having any clinically significant ECG abnormality, as assessed by the Investigator, will not be allowed to continue in the study.

### **11.1.7. Clinical Laboratory Assessments**

When a laboratory assessment that is listed in the inclusion/exclusion criteria is outside of a protocol-specified range at screening, the assessment may be repeated once prior to study number assignment. If the repeat value remains outside of protocol-specified ranges, the subject will be excluded from the study.

Clinically relevant deviations from the normal range for laboratory test results should be evaluated for criteria defining an AE and reported as such.

Sample collection and handling information for all laboratory evaluations are provided in the Laboratory Reference Manual.

#### **11.1.7.1. Hematology**

Hematology assessments will include complete blood count (CBC), including platelet count and leukocyte differential, which will be performed as outlined in the Schedule of Assessments ([Table 6](#) for Part A and [Table 7](#) for Part B).

#### **11.1.7.2. Clinical Chemistry**

Clinical chemistry evaluations will include sodium, potassium, chloride, bicarbonate, blood urea nitrogen, creatinine, glucose, calcium, AST, ALT, alkaline phosphatase, albumin, total and indirect bilirubin, and will be measured per the Schedule of Assessments ([Table 6](#) for Part A and [Table 7](#) for Part B). Clinical chemistry assessments will be done on the morning of the assessment day.

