associated with severe sickle cell crises and death in patients with SCD or trait. Licensed in the US since 2008, plerixafor (Mozobil®, Genzyme) is a small molecule, reversible antagonist of chemokine receptor 4 (CXCR4), currently indicated to be used in combination with G-CSF to mobilize HSCs to the peripheral blood for collection and subsequent autologous transplantation in patients with multiple myeloma and non-Hodgkin's lymphoma. Plerixafor acts by disrupting binding to the receptor's cognate ligand, stromal-derived factor-1α (SDF-1α) chemokine ligand 12 (CXCL12), thereby resulting in mobilization of CD34+ HSCs into the peripheral blood. More recently, plerixafor alone has demonstrated efficacy in the mobilization of sufficient HSC for collection in patient populations, including SCD. However, as many as 75% of patients with SCD require 2 or more cycles of multi-day plerixafor administration and apheresis in order to collect sufficient HSCs for genetic modification and infusion, and vaso-occlusive crisis remains a risk with each mobilization and apheresis procedure, with approximately 30% of plerixafor-mobilized patients reported to have experienced VOEs of at least Grade 3 severity during and after harvesting, and approximately 20% of patients reported to have experienced serious vaso-occlusive pain within 2 days post-procedure. Hypomagnesemia, hypokalemia, and hypocalcemia have also been reported commonly among patients with SCD mobilized with plerixafor, although most events were Grade 1 or 2 in severity. Approximately half of patients with SCD require opioid medications within a week prior or subsequent to mobilization and apheresis. Nonetheless, mobilization with plerixafor seems to result in an apheresis product superior to bone marrow harvest, based on the concentration of high-quality CD34+ HSCs most suitable for *ex vivo* manipulation and autologous transplantation.

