**Table 4: Part A Objectives and Endpoints**

Part A Primary Objectives	Part A Primary Endpoints
To characterize the efficacy of a single dose of MGTA-145 and plerixafor for HSC mobilization and apheresis collection in patients with SCD	
 
Determination of the yield of CD34+ cells (CD34+ cells/kg) after 1 dose of MGTA-145 and plerixafor followed by apheresis
 

To characterize the safety and tolerability of MGTA-145 in patients with SCD	
 
Incidence of TEAEs, including drug-related TEAEs, <math>\geq</math>Grade 3 TEAEs, TESAEs, and TEAEs leading to study drug discontinuation
 
Incidence of treatment-emergent <math>\geq</math>Grade 3 clinical laboratory abnormalities
 
Clinically significant changes from baseline in vital signs and laboratory parameters (e.g., serum chemistry, hematology)
 

To measure the mobilization effects of single-day dosing with MGTA-145 and plerixafor in the peripheral blood in patients with SCD	
 
Determination of peak peripheral blood CD34+ counts
 

To characterize the PK profile of MGTA-145 in patients with SCD	
 
Determination of PK exposures
 

To characterize the immunogenicity of MGTA-145 in patients with SCD	
 
Presence and titers of anti-drug antibodies
 

Part A Exploratory Objectives	Part A Exploratory Endpoints
To characterize the phenotype and function of cells collected by apheresis in patients with SCD	
 
Flow cytometric characterization of cells collected following MGTA-145 and plerixafor mobilization and apheresis
 
Characterization of hematopoietic cell function by mouse engraftment studies and/or colony formation assays
 

To assess gene-modifying potential of mobilized CD34 + cells in patients with SCD	
 
Assessment of ability to select and gene-modify CD34+ cells
 

HSC=hematopoietic stem cells; PD=pharmacodynamic(s); PK=pharmacokinetic(s); SCD=sickle cell disease; TEAE=treatment-emergent adverse event; TESAE=treatment-emergent serious adverse event	

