**Figure 1: Part A (Single Dose) and Part B (Single Dose on 2 Consecutive Days)**

**Table 6: Schedule of Assessments: Part A (Single Dose)**

Study Period Procedures	Screening	Baseline	Mobilization /Apheresis	1-week follow-up (Day 7 to 10) b	End of Study (Day 30) b
	Day -30 to -2	Day -1	Day 1		
Informed consent	X				
Medical history	X	X			
Inclusion/exclusion criteria review	X				
Height		X			
Weight		X		X	
Physical examination	X	X		X	
Symptom-directed physical examination			X		
Vital signs a	X	X	X	X	
Serology c	X				
Serum or urine $\beta$ -hCG (females)	X	X			
12-lead ECG	X				
Urinalysis		X	X	X	
Chemistry d	X	X	X	X	
Hematology e	X	X	X	X	
Anti-drug antibodies		X		X	
Plerixafor administration			X		
MGTA-145 administration f			X		
Apheresis procedure			X		
Apheresis yield g			X		
PROMIS and ASCQ-Me questionnaires h			X	X	
Non-serious AEs and SAEs i	X	X	X	X	X j
Concomitant medications	X	X	X	X	X j

AE=adverse event; ASCQ-Me=Adult Sickle Cell Quality of Life Measurement Information; BPI=Brief Pain Inventory;  $\beta$ -hCG=beta-human chorionic gonadotropin; CFU= colony-forming unit; ECG=electrocardiogram; PK=pharmacokinetics; NRS=Numeric Rating Scale; SAE=serious adverse event

a Vital sign measurements will be taken in the sitting position after the subject has been resting for 5 minutes. Vital signs should be taken before any blood samples are drawn.

b If a subject does not complete dosing, there will not be follow-up visits. If a subject received MGTA-145 but did not complete apheresis, then follow-up visits are required.

c All subjects enrolled in Parts A will be screened for human immunodeficiency virus (HIV), hepatitis B surface antigen (HBsAg), human T-cell leukemia virus (HTLV), and hepatitis C virus (HCV) at the screening visit. Subjects who are HCV antibody positive must have a HCV ribonucleic acid (RNA) polymerase chain reaction (PCR) test.

d Clinical chemistry consists of sodium, potassium, chloride, bicarbonate, blood urea nitrogen, creatinine, glucose, calcium, aspartate aminotransferase (AST), alanine aminotransferase (ALT), alkaline phosphatase, albumin, total and indirect bilirubin. Clinical chemistry sample collection should be done prior to dosing on Day 1. All other clinical chemistry sample collections will be done on the morning of the assessment day.

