e Hematology is complete blood count (CBC) with platelets and leukocyte differential. Hematology sample collection should be done prior to dosing on Day 1 and Day 2. All other hematology sample collections will be done on the morning of the assessment day.

f MGTA-145 is to be administered via a 3 to 10-minute IV infusion, approximately 2 hours after plerixafor SC injection. Instructions regarding administration are provided in the Study Pharmacy Manual.

g Total nucleated cell count and CD34+ cell count in absolute numbers and per kg.

h ASCQ-Me® and PROMIS® questionnaires will be completed prior to dosing on Day 1.

i Collection of non-serious AEs and SAEs will begin once the Informed Consent Form (ICF) has been signed. Any SAE occurring after the reporting period must be promptly reported if a causal relationship to study drugs is suspected.

j End-of-study visit phone call will occur 30 days ( $\pm 3$  days) after the last dose of MGTA-145 was received, to assess adverse events and concomitant medications.

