#### **11.1.7.3. Urinalysis**

Per the Schedule of Assessments ([Table 6](#) for Part A and [Table 7](#) for Part B), urinalysis, conducted by dipstick, will assess pH, protein, glucose, ketone, urobilinogen, bilirubin, blood, specific gravity, nitrite, and leukocytes.

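### Hypomagnesemia is named as common after plerixafor mobilization in sickle cell disease, but the scheduled chemistry panel omits magnesium, so its capture is left to chance

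*Protocol*

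**What the plan says.** Section 4 (Introduction) describes the safety background of plerixafor mobilization in this population: "Hypomagnesemia, hypokalemia, and hypocalcemia have also been reported commonly among patients with SCD mobilized with plerixafor, although most events were Grade 1 or 2". Every subject in both parts receives plerixafor and is planned to undergo apheresis.

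Section 11.1.7.2 gives the chemistry panel: "Clinical chemistry evaluations will include sodium, potassium, chloride, bicarbonate, blood urea nitrogen, creatinine, glucose, calcium, AST, ALT, alkaline phosphatase, albumin, total and indirect bilirubin". Table 6, footnote d (Part A) gives the same analytes in closed form, beginning "Clinical chemistry consists of sodium, potassium, chloride, bicarbonate, blood urea nitrogen, creatinine, glucose, calcium, aspartate aminotransferase (AST". Table 7, footnote e (Part B) repeats it.

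Tables 4 and 5 make two laboratory-based measures primary safety endpoints in each part. One is the incidence of treatment-emergent "Grade 3 clinical laboratory abnormalities" (Grade 3 or higher). The other is clinically significant change from baseline in laboratory parameters, with serum chemistry given as an example. Sections 6.3 and 13.5 have the DMC review safety after each Part A cohort.

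**The concern.** The protocol names three electrolyte abnormalities to be expected with the background drug and schedules tests for two of them. The one left out is the first on its own list. What is drawn is fixed by the protocol, and no analysis plan can summarize a value that was never collected.

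The study has no control arm, so its safety results will be read against what is known of plerixafor alone, as the stopping rules in Section 6.6 already do for vaso-occlusive events. For magnesium no such reading is possible from scheduled data. There would be no baseline, no later value and no basis for a laboratory-abnormality row. A reader of the report could take that silence for absence.

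Section 6.6.1.3 also pauses dosing for DMC review after a drug-related event of Grade 3 or higher, apart from listed exemptions that do not include hypomagnesemia. The scheduled tests would not bring such an event to light.

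**Working it through.** The protocol states no figure on this point, so there is none to reproduce. The check compares the lists and then counts the draws.

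**1. Named abnormalities against the panel**

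| Abnormality named in Section 4 | Analyte | 11.1.7.2 | Table 6, footnote d | Table 7, footnote e |
|---|---|---|---|---|
| Hypomagnesemia | Magnesium | absent | absent | absent |
| Hypokalemia | Potassium | listed | listed | listed |
| Hypocalcemia | Calcium | listed | listed | listed |

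The omission is the same in all three places, so it is not a slip in one copy. Section 11.1.7.2 says what the panel will include, which could be read as open. Both table footnotes say what it consists of, which closes the list.

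**2. Other scheduled tests**

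- Hematology: "Hematology is complete blood count (CBC) with platelets and leukocyte differential".
- Urinalysis: "conducted by dipstick, will assess pH, protein, glucose, ketone, urobilinogen, bilirubin, blood, specific gravity, nitrite, and leukocytes".
- Serology covers viruses only. The remaining scheduled samples are for pregnancy testing, anti-drug antibodies, pharmacokinetics and cell counts.

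None measures magnesium, and the protocol does not name magnesium as a test anywhere.

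**3. Scheduled chemistry draws (Tables 6 and 7)**

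- Part A: screening, Day -1, Day 1 before dosing, and the 1-week visit (Day 7 to 10), which makes 4. After first dosing: 1.
- Part B: screening, Day -1, Day 1 before dosing, Day 2 before dosing, and the 1-week visit (Day 8 to 11), which makes 5. After first dosing: 2.

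**4. What adding magnesium at these draws would yield**

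This takes the planned 7 to 11 evaluable subjects in Part A and 3 in Part B, all attending every visit:

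- All values: (7 × 4) + (3 × 5) = 43, up to (11 × 4) + (3 × 5) = 59. The protocol as written schedules none of these.
- Values after first dosing: (7 × 1) + (3 × 2) = 13, up to (11 × 1) + (3 × 2) = 17.

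Each subject would gain a baseline and a 1-week value. Each Part B subject would also gain a value between the two mobilization days. No scheduled draw falls soon after apheresis in Part A, or after the second session in Part B.

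**The case against.** The strongest reply is that the omission has little practical effect. Several parts of it stand.

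- **Other routes into the data.** Section 11.2.2 counts an abnormal laboratory value as an adverse event if it causes symptoms, is clinically significant or needs treatment, and does not limit this to scheduled tests. Section 11.1.7 likewise sends clinically relevant deviations to adverse event reporting. Subjects are observed on site around apheresis, care follows local practice, and concomitant medication is recorded through the end of study. A reader might therefore infer too much from the gap, namely that the trial is unable to find hypomagnesemia or must report zero events. The documents do not support that. What is lost is systematic capture with a baseline.
- **Severity.** Section 4 says most of these electrolyte events were Grade 1 or 2. The Grade 3 or higher endpoint would pass over most of them even with magnesium measured. The loss bears more on clinically significant change from baseline.
- **Timing.** With so few draws after dosing, adding the analyte would not reliably show a transient fall around apheresis. Potassium and calcium, which are measured, share this limit.
- **No broken commitment.** Section 4 is background. No endpoint, eligibility criterion or stopping rule names magnesium, so no two provisions contradict each other.
- **No rate.** The protocol gives no percentage for how common hypomagnesemia is, and none for events that are both Grade 3 or higher and drug-related. A count of affected subjects, or of missed pauses under Section 6.6.1.3, cannot be drawn from the documents.

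These replies limit the consequence. They do not explain why two of the three named abnormalities are measured and the third is not.

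**Conclusion.** The point holds as an inexpensive improvement to safety measurement. One of three electrolyte abnormalities that the protocol itself calls common is missing from all scheduled chemistry draws, 4 per subject in Part A and 5 in Part B. The two laboratory-based primary safety endpoints and the DMC therefore have no systematic magnesium data, and any case depends on a site testing on its own initiative and reporting an adverse event.

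The omission is certain from the text. The number of events missed is unknown, because the documents give no rate. The gap does not touch the CD34+ yield endpoint or the rules on vaso-occlusive events.

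The conclusion rests on reading the table footnotes as closed lists, and on the laboratory manual, which is not at hand, adding no analyte.

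**What to change.** Add serum magnesium to the panel in Section 11.1.7.2, Table 6 footnote d and Table 7 footnote e, at the chemistry draws already scheduled. Include it in the Grade 3 or higher laboratory summary, the change-from-baseline summary and the data sent to the DMC. If the sponsor prefers to leave it out, the protocol should say why, given Section 4.

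The cost is one further analyte on blood already drawn (about 43 to 59 results in evaluable subjects, plus any from screen failures), three wording changes and one eCRF field. A few extra low-grade findings may follow.

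The protocol or the report should also acknowledge that only one draw in Part A and two in Part B follow first dosing, so short-lived changes in magnesium, potassium or calcium around apheresis may go unrecorded.

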#### **11.1.7.3. Urinalysis**

Per the Schedule of Assessments ([Table 6](#) for Part A and [Table 7](#) for Part B), urinalysis, conducted by dipstick, will assess pH, protein, glucose, ketone, urobilinogen, bilirubin, blood, specific gravity, nitrite, and leukocytes.

#### **11.1.7.4. Virus Serology**

All study subjects enrolled in Parts A and B will be screened for HIV, hepatitis B surface antigen (HbsAg), HTLV, and HCV at the screening visit. Subjects who are HCV-antibody positive must have a negative HCV ribonucleic acid (RNA) polymerase chain reaction (PCR) test in order to be considered eligible for study participation.

#### **11.1.7.5. Pregnancy Screen**

All females of childbearing potential enrolled in Parts A and B will have a serum or urine beta-human chorionic gonadotropin ( $\beta$ -hCG) pregnancy test performed at the screening visit and at baseline (Day -1).

#### **11.1.8. Patient Surveys**

Patient Survey forms used in the study as outlined in the Schedule of Assessments ([Table 6](#) for Part A and [Table 7](#) for Part B) are provided in Appendix [Section 18.2](#).

##### **11.1.8.1. ASCQ-ME®**

The Adult Sickle Cell Quality of Life Measurement Information System (ASCQ-Me®) is a patient-reported outcome measurement system that evaluates the physical, mental, and social well-being of adults with SCD across 5 domains, including emotional impact, social functioning, pain, stiffness, and sleep functioning.

For all subjects enrolled in Parts A and B, the ASCQ-Me® will be performed prior to dosing on Day 1 and at the 1-week follow-up visit (Day 7-10).

#### **11.1.8.2. PROMIS®**

The Patient-Reported Outcomes Measurement Information System (PROMIS®) evaluates the physical, mental, and social well-being of adults and children living with chronic conditions.

Among the 7 primary PROMIS domains (physical function, anxiety, depression, fatigue, sleep disturbance, ability to participate in social roles and activities, and pain interference), only the pain intensity and pain interference domains are to be performed in this study, prior to dosing on Day 1 and at the 1-week follow-up visit (Day 7 to 10).

#### **11.1.9. EOS Phone Visit**

End-of-study phone visit will occur 30 days ( $\pm 3$  days) after the last dose of MGTA-145 was received, to assess adverse events and concomitant medications.

### **11.2. Adverse Events and Serious Adverse Events**

#### **11.2.1. Adverse Events**

Collection of non-serious AEs and serious adverse events (SAEs) will begin once the ICF is signed and continue until the EOS visit. Non-serious AEs and SAE reporting will end at the EOS visit. Any SAE occurring after the reporting period must be promptly reported if a causal relationship to study drugs is suspected.

#### **11.2.2. Adverse Event Definition**

An AE is any untoward medical occurrence (i.e., any unfavorable and unintended sign [including abnormal laboratory findings], symptom, or disease) in a subject or clinical investigation subject administered a medicinal product. Therefore, an AE may or may not be temporally or causally associated with the use of a medicinal (investigational) product.

The occurrence of AEs should be sought by non-directive questioning of the subject at each visit during the study. Adverse events also may be detected when they are suspected by the subject or subject's family during or between visits or through physical examination, laboratory test, or other assessments.

Abnormal laboratory values or test results constitute AEs only if they fulfill at least one of the following criteria:

- Induce clinical signs or symptoms
- Are considered clinically significant
- Require therapy or medical intervention

Clinically significant abnormal laboratory values or test results should be identified through a review of values outside of normal ranges/clinically notable ranges, significant changes from baseline values or the previous visit, or values which are considered to be non-typical in subjects with underlying disease. Investigators have the responsibility for managing the safety of individual subjects and identifying and documenting AEs.

From the signing of informed consent, non-serious AEs and SAEs must be recorded on the AE eCRF for subjects who enroll in the study. The Investigator should attempt to establish a diagnosis of the event based on signs, symptoms and/or other clinical information. In such cases, the diagnosis should be documented as the AE and/or SAE rather than as the individual signs/symptoms. The AEs should be accompanied by the following information:

1. The CTCAE Grade (version 5.0)

If CTCAE grading does not exist for an AE (and this is rare), use:

Grade 1=mild

Grade 2=moderate

Grade 3=severe

Grade 4=life-threatening

Grade 5- death

2. Relationship to the study treatments (definitely related, probably related, possibly related, unlikely related, not related).
3. Duration (start and end dates) or if the event is ongoing an outcome of not recovered/not resolved should be reported.
4. Whether it constitutes an SAE (see [Section 11.2.4](#) for the definition of SAE).
5. Action taken regarding study treatments.
6. Outcome (not recovered/not resolved; recovered/resolved; recovered/resolved with sequelae; fatal; or unknown). Death is an outcome of an event. The event that resulted in death must be recorded on the appropriate eCRF and reported as an SAE.

Treatment related AEs and all SAEs should be followed until resolution, stabilization, or until it is judged to be permanent, and an assessment should be made at each visit (or more frequently, if necessary) of any changes in severity, the suspected relationship to the study drug, the interventions required to treat it, and the outcome.

Information about common side effects already known about the investigational drug can be found in the Investigator's Brochure (IB) or will be communicated between IB updates in the form of Investigator Notifications. Information regarding common side effects of plerixafor can be found in the product's package insert. This information will be included in the subject's informed consent and should be discussed with the subject during the study as needed.

